### **Overview of the Oral Formulation of ixazomib**

The safety profile indicates that oral ixazomib is generally well tolerated with predominant toxicities largely reversible, able to be monitored by routine clinical examinations and manageable by dose reductions, discontinuation, or standard supportive care. From experience from phase 1 through 2 studies the major toxicities can be managed to allow repeat treatment cycles over periods extending beyond 24 months.

Relapsed MM: Single-agent, Weekly ixazomib (Study C16004):

Study C16004 is an open-label, dose-escalation, phase 1 study of ixazomib administered weekly on Days 1, 8, and 15 of a 28-day cycle in adult patients with RRMM. Patients with MM enrolled in the dose-escalation component of the study have relapsed following at least 2 lines of therapy, which must have included bortezomib, thalidomide (or lenalidomide), and corticosteroids. In this study, 2 of 3 patients experienced protocol-defined DLTs (Grade 3 rash and Grade 3 nausea, vomiting, and diarrhea) at a dose of 3.95 mg/m^2. As per protocol, subsequent patients were treated at 1 dose level below (2.97 mg/m^2) where 1 of 6 patients experienced a DLT (Grade 3 nausea, vomiting, and diarrhea). The MTD of weekly oral ixazomib was determined to be 2.97 mg/m^2.

[figure not shown]
Once the MTD was established, cohorts of patients representing the heterogeneous patient population currently seen in clinical practice were enrolled in order to further evaluate the safety, tolerability, efficacy, PK, and pharmacodynamics of oral ixazomib and included:

1. Relapsed and Refractory expansion cohort [refractory is defined as disease progression while on therapy or within 60 days after the last dose of therapy];
2. Carfilzomib expansion cohort
3. Proteasome Inhibitor-Naïve expansion cohort
4. VELCADE-Relapsed expansion cohort

Sixty patients with relapsed and/or refractory multiple myeloma were enrolled. The MTD was determined to be 2.97 mg/m^2. Dose-limiting toxicities were grade 3 nausea, vomiting, and diarrhea in 2 patients, and grade 3 skin rash in 1 patient. Common drug-related adverse events were thrombocytopenia (43%), diarrhea (38%), nausea (38%), fatigue (37%), and vomiting (35%). The observed rate of peripheral neuropathy was 20%, with only 1 grade 3 event reported. Nine (18%) patients achieved a partial response or better, including 8 of 30 (27%) evaluable patients treated at the MTD. Pharmacokinetic studies suggested a long terminal half-life of 3.6 to 11.3 days, supporting once-weekly dosing.

***Newly Diagnosed Multiple Myeloma (C16005):***

In Study C16005, ixazomib is given weekly (Days 1, 8, and 15), in combination with lenalidomide (Days 1-21), and dexamethasone (Days 1, 8, 15, and 22) in a 28-day cycle. Patients with newly diagnosed MM were enrolled and treated with oral ixazomib (days 1, 8, and 15) plus lenalidomide 25 mg (days 1-21) and dexamethasone 40 mg (days 1, 8, 15, 22) for up to twelve 28-day cycles, then maintenance therapy with ixazomib (same schedule) every 28 days until progression. Patients were allowed to undergo stem cell collection after 3 cycles and discontinue for autologous stem cell transplant (ASCT) after 6 cycles. Overall, 65 patients were enrolled, 15 in Phase 1 and 50 in Phase 2. Patients received a median of 6 cycles (range 1-19) with 27 (42%) remaining on treatment as of November 2012. Of those who have undergone stem cell mobilization, a median yield was  $11.3 \times 10^6$  CD34+ cells/Kg (range 5-28). ixazomib MTD was established as 2.97 mg/m^2 and RP2D was selected as 2.23 mg/m^2; RP2D translates to a 4.0 mg fixed dose based on population PK results. Among the 64 evaluable patients, the overall response rate was 92%, including 55% VGPR and 23% CR (Figure 3 below). Median time to first response was 0.92 months (range 0.89-6.44).

### Potential Risks and Benefits of ixazomib:

Please refer to the current ixazomib Investigator's Brochure (IB)

#### 1.4 Lenalidomide in myeloma

Lenalidomide has significant activity in the setting of multiple myeloma; both in relapsed and in newly diagnosed disease. Initial phase I/II study of lenalidomide in relapsed myeloma determined the ideal dose to be 25 mg once daily given for 3 of 4 weeks. The initial trial in the relapsed disease also demonstrated increased activity in combination with pulsed doses of dexamethasone. These findings led to the initial trials of the combination in newly diagnosed disease as well as randomized trials of the combination in relapsed myeloma. In the phase III trials of lenalidomide and dexamethasone, the combination was demonstrated to be superior to dexamethasone in terms of response rates and progression free and overall survival. The initial phase II study of lenalidomide and dexamethasone in newly diagnosed myeloma, conducted at the Mayo Clinic, also employed the combination of lenalidomide and pulsed dose dexamethasone (40 mg daily on four days on four days off schedule) for the first four cycles followed by 40 mg weekly for the subsequent cycles. The phase II study demonstrated significant response rates and long term follow up demonstrated sustained responses and 1-year survival rates of over 90%. The subsequent phase III trial in the ECOG (E4A03) compared the same dosing strategy to one that employed a lower dose of dexamethasone (40 mg weekly) right from the start of therapy. The results of the trial demonstrated a superior overall survival for the lower dose dexamethasone arm.

#### 1.5 Daratumumab in myeloma

Daratumumab is a human IgG1κ monoclonal antibody (mAb) that binds with high affinity to a unique epitope on CD38, a transmembrane glycoprotein. It is a targeted immunotherapy directed towards tumor cells that express high levels of CD38, such as plasma cells from patients with multiple myeloma. This target is distinct from those of other approved agents for multiple myeloma therapy. Daratumumab is currently approved for treatment of relapsed myeloma, that are refractory to a proteasome inhibitor and an IMiD. It is not approved for initial therapy of myeloma, and hence considered investigational for the current trial.

#### *Nonclinical Studies with daratumumab*

Based on preclinical data, daratumumab may utilize multiple effector cell functions, resulting in immune mediated killing of tumor cells. In ex vivo experiments utilizing human bone marrow

stromal cells co-cultured with primary multiple myeloma cells, complement-dependent cytotoxicity (CDC) occurs rapidly and demonstrates maximal myeloma cell killing by daratumumab within 1 hour of antibody-mediated activation of the complement proteins. Daratumumab-induced antibody-dependent cell-mediated cytotoxicity (ADCC) is slower in its action, with maximal ADCC by daratumumab observed at 4 hours in vitro. Daratumumab has also been shown to induce antibody-dependent cellular phagocytosis (ADCP) in the presence of macrophages within 4 hours in vitro. The precise role of some or all of these effector functions in reducing tumor burden in patients is unknown. In toxicology studies in cynomolgus monkeys and chimpanzees, the major observed toxicities were cytokine release syndrome and thrombocytopenia. A minor decrease in red blood parameters was also observed. Cytokine release was seen only following the first dose and was markedly reduced following implementation of a 10-mg predose of daratumumab. The effect on platelets and red blood cells was reversible. For the most comprehensive nonclinical and clinical information as well as Reference Safety Information regarding daratumumab, refer to the latest version of the Investigator's Brochure (Daratumumab IB).

### ***Clinical studies with daratumumab***

**Single agent studies:** Two large single agent studies have been reported to date; GEN501 and MMY2002. In the GEN501 study, daratumumab was administered at doses of 0.005 to 24 mg per kilogram of body weight during the dose escalation phase. No maximum tolerated dose was identified. In the dose-expansion phase, 30 patients received 8 mg per kilogram of daratumumab and 42 received 16 mg per kilogram, administered once weekly (8 doses), twice monthly (8 doses), and monthly for up to 24 months. In the expansion phase, the median time since diagnosis was 5.7 years. Patients had received a median of four prior treatments; 79% of the patients had disease that was refractory to the last therapy received (64% had disease refractory to proteasome inhibitors and immunomodulatory drugs and 64% had disease refractory to bortezomib and lenalidomide), and 76% had received autologous stem-cell transplants. Infusion-related reactions were mild (71% of patients had an event of any grade, and 1% had an event of grade 3), with no dose-dependent adverse events. The most common adverse events of grade 3 or 4 (in  $\geq 5\%$  of patients) were pneumonia and thrombocytopenia. The overall response rate was 36% in the cohort that received 16 mg per kilogram (15 patients had a partial response or better, including 2 with a complete response and 2 with a very good partial response) and 10% in the cohort that received 8 mg per kilogram (3 had a partial response). In the cohort that received 16 mg per kilogram, the median progression-free survival was 5.6 months (95% confidence interval [CI], 4.2 to 8.1), and 65% (95% CI, 28 to 86) of the patients who had a response did not have progression at 12 months.

In the MMY2002 study, patients with multiple myeloma who were previously treated with at least three lines of therapy (including proteasome inhibitors and immunomodulatory drugs), or were refractory to both proteasome inhibitors and immunomodulatory drugs, were randomized to receive intravenous daratumumab 8 mg/kg or 16 mg/kg in the initial part of the study. Patients received 8 mg/kg every 4 weeks, or 16 mg/kg per week for 8 weeks (cycles 1 and 2), then every 2 weeks for 16 weeks (cycles 3–6), and then every 4 weeks thereafter (cycle 7 and higher). In the second part of the study, the dose of 16 mg/kg was taken forward. One-hundred-six patients with a median of five previous lines of therapy (range 2–14) were treated at the 16-mg/kg dose. 85 (80%) patients had previously received autologous stem cell transplantation, 101 (95%) were refractory to the most recent proteasome inhibitors and immunomodulatory drugs used, and 103 (97%) were refractory to the last line of therapy. Overall, responses were seen in 31 patients (29.2%);—three (2.8%) with a stringent CR, ten (9.4%) with a VGPR, and 18 (17.0%) with a PR. Median duration of response was 7.4 months (95% CI 5.5—not estimable) and

progression-free survival was 3·7 months and the 12-month overall survival was 64·8%. Daratumumab was well tolerated; fatigue (40%) and anemia (33%) were the most common adverse events.

**Daratumumab-lenalidomide combinations:** Preclinically, using bone marrow mononuclear cells from patients with multiple myeloma, increased killing of tumor cells was demonstrated when daratumumab was combined with lenalidomide as compared with that of either agent alone.

In an open-label phase 1/2 study DARA 2-16 mg/kg was combined with standard dose of lenalidomide and dexamethasone, leading to a recommended phase 2 dose of daratumumab 16 mg/kg along with lenalidomide 25 mg days 1-21 and dexamethasone 40 mg weekly.

Daratumumab 16 mg/kg was administered weekly during the first two 28-day cycles, every other week during Cycles 3 through 6, and monthly in Cycle 7 and beyond until disease progression or unacceptable toxicity. LEN 25 mg was administered orally on Days 1 through 21 of each cycle, and DEX 40 mg was given weekly. Thirty two patients with median of 2 prior lines of therapy were enrolled.

The most common (>25%) TEAEs included neutropenia (81%), muscle spasms (44%), cough (38%), diarrhea (34%), fatigue and hypertension (28% each). Eighteen (56%) patients had IRRs and these were generally mild to moderate and occurred mostly during the first cycle. IRRs included cough (25%), allergic rhinitis, nausea, and vomiting (9% each), as well as dyspnea, nasal congestion, and hypertension (6% each). The overall response rate was 88%, with 11 (34%) partial responses and 17 (53%) ≥very good partial responses (VGPRs) that included 7 (22%) stringent complete responses, 1 (3%) complete response, and 9 (28%) VGPRs. The median time to first and best response was 1 month and 4.5 months, respectively. Results of this study confirm the efficacy of combining daratumumab with lenalidomide and dexamethasone. A large phase 3 trial of Daratumumab and Rd versus Rd has completed accrual.

**1.6 Rationale for the current trial:** Ixazomib in combination with lenalidomide and dexamethasone results in high response rates and deep responses in patients with newly diagnosed myeloma. It is well tolerated and patients are able to stay on it long term as a maintenance therapy. More recently, addition of daratumumab to lenalidomide and dexamethasone has resulted in significant activity in relapsed myeloma. The combination of the ixazomib, lenalidomide, daratumumab and dexamethasone presents the potential to further enhance the response to therapy with four different drug classes with no significant overlapping toxicities. We hypothesize that this combination will lead to deep response including a higher proportion of MRD negative disease that will translate into longer survival in these patients.

**Rationale for Arm B:** Long term therapy with dexamethasone is associated with various side effects including osteoporosis, adrenal suppression, muscle weakness, and increased risk of opportunistic infections. Given the efficacy of the daratumumab, ixazomib and lenalidomide, it is likely we will be able to decrease the dexamethasone doses and potentially eliminate it after the initial cycles. We will add a similar cohort of patients and treat them with dexamethasone only for the first two cycles of treatment and then discontinue. The endpoints of the trial will not be altered.

**2.0 Goals**

## 2.1 Primary

To determine the complete response rate (CR) of the four-drug combination of Ixazomib, lenalidomide, dexamethasone and daratumumab in patients with previously untreated symptomatic MM.

## 2.2 Secondary

2.21 To determine the overall response rate (ORR), and very good partial response (VGPR) rate with the four drug combination of ixazomib, lenalidomide, dexamethasone and daratumumab, when used as initial therapy in patients with previously untreated symptomatic MM

2.22 To determine the progression free survival and overall survival among patients with previously untreated symptomatic MM following treatment with the four drug combination of Ixazomib, lenalidomide, dexamethasone and daratumumab followed by ixazomib and daratumumab maintenance till progression.

2.22 To determine the toxicities associated with the four drug combination of Ixazomib, lenalidomide, dexamethasone and daratumumab in patients with previously untreated symptomatic MM.

## 2.3 Correlative Research

2.31 To examine the proportion of MRD negativity following induction therapy with the four-drug combination of Ixazomib, lenalidomide, dexamethasone and daratumumab

2.32 To assess the quality of life using patient completed FACT/GOG questionnaires.

**3.0 Patient Eligibility**

## 3.1 Inclusion Criteria

3.11 Age  $\geq$ 18 years.

3.12 The following laboratory values obtained  $\leq$ 14 days prior to registration.

- Calculated creatinine clearance (using Cockcroft-Gault equation below)\*  
 $\geq$ 30 mL/min
- Absolute neutrophil count (ANC)  $\geq$ 1500/mm^3
- Untransfused Platelet count  $\geq$ 75000/mm^3
- Hemoglobin  $\geq$ 8.0 g/dL
- Total bilirubin  $\leq$  1.5 x ULN
- ALT and AST  $\leq$  2.5 x ULN

\*Cockcroft-Gault Equation:

Creatinine clearance for males =  $(140 - \text{age})(\text{actual body weight in kg})/(72)(\text{serum creatinine in mg/dL})$

Creatinine clearance for females =  $(140 - \text{age})(\text{actual body weight in kg})(0.85)/(72)(\text{serum creatinine in mg/dL})$

3.13 Measurable disease of multiple myeloma as defined by at least ONE of the following:

- Serum monoclonal protein  $\geq 1.0$  g/dL (see Section 11.1 for definition)
- $\geq 200$  mg of monoclonal protein in the urine on 24 hour electrophoresis
- Serum immunoglobulin free light chain  $\geq 10$  mg/dL AND abnormal serum immunoglobulin kappa to lambda free light chain ratio.

3.14 ECOG performance status (PS) 0, 1 or 2 (Appendix IV)

3.15 Previously untreated for myeloma or have received no more than one cycle of any treatment regimen. NOTE: Prior radiation therapy for the treatment of solitary plasmacytoma is permitted. Prior therapy with clarithromycin, DHEA, anakinra, pamidronate or zoledronic acid is permitted. Any additional agents not listed must be approved by the Principal Investigator.

3.16 Provide informed written consent.

3.17 Negative pregnancy test done  $\leq 7$  days prior to registration, for women of childbearing potential only.

3.18 Willing to follow strict birth control measures.  
Female patients: If they are of childbearing potential, agree to one of the following:

- Practice 2 effective methods of contraception, at the same time, from the time of signing the informed consent form through 90 days after the last dose of study drug, AND must also adhere to the guidelines of any treatment-specific pregnancy prevention program, if applicable, OR
- Agree to practice true abstinence when this is in line with the preferred and usual lifestyle of the subject. (Periodic abstinence [e.g., calendar, ovulation, symptothermal, post-ovulation methods] and withdrawal are not acceptable methods of contraception.)

Male patients: even if surgically sterilized (i.e., status post-vasectomy), must agree to one of the following:

- Agree to practice effective barrier contraception during the entire study treatment period and through 90 days after the last dose of study drug, OR
- Must also adhere to the guidelines of any treatment-specific pregnancy prevention program, if applicable, OR
- Agree to practice true abstinence when this is in line with the preferred and usual lifestyle of the subject. (Periodic abstinence [e.g., calendar, ovulation, symptothermal, post-ovulation methods] and withdrawal are not acceptable methods of contraception.)

3.19a Negative hepatitis B test (defined by a negative test for hepatitis B surface antigen [HBsAg], or antibodies to hepatitis B surface and/or core antigens [antiHBs or antiHBc] (added as of addendum 9))  
**Note:** Patients with serologic findings suggestive of HBV vaccination (antiHBs positivity as the only serologic marker) AND a known history of prior HBV vaccination do not need to be tested for HBV DNA by PCR. Those who are PCR positive will be excluded.

3.19b Willing to return to enrolling institution for follow-up (during the Active Monitoring Phase of the study).

3.19c Willing to follow the requirements of the Revlimid REMS program

3.19d Willing to provide bone marrow and blood samples for planned research

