### 3.2 Exclusion Criteria

3.21 MGUS or smoldering myeloma.

3.22 Diagnosed or treated for another malignancy  $\leq$  2 years prior to registration or previously diagnosed with another malignancy and have any evidence of residual disease. **NOTE:** Patients with nonmelanoma skin cancer or carcinoma in situ of any type are not excluded if they have undergone complete resection.

3.23 Any of the following because this study involves an investigational agent whose genotoxic, mutagenic and teratogenic effects on the developing fetus and newborn are unknown:

- Pregnant women
- Nursing women
- Men or women of childbearing potential who are unwilling to employ adequate contraception

3.24 Other concurrent chemotherapy, or any ancillary therapy considered investigational. **NOTE:** Bisphosphonates are considered to be supportive care rather than therapy, and are thus allowed while on protocol treatment.

3.25 Peripheral neuropathy  $\geq$  Grade 2 on clinical examination or grade 1 with pain during the screening period.

3.26 Major surgery  $\leq$  14 days prior to registration.

3.27 Systemic treatment with strong CYP3A4 inducers (rifampin, rifapentine, rifabutin, carbamazepine, phenytoin, phenobarbital, St. John's wort)  $\leq$  14 days prior to registration.

3.28 Evidence of current uncontrolled cardiovascular conditions, including hypertension, cardiac arrhythmias, congestive heart failure, unstable angina, or myocardial infarction  $\leq$  6 months. Note: Prior to entry, any ECG abnormality at screening must be documented by the investigator as not medically relevant.

3.29a Radiotherapy  $\leq$  14 days prior to registration. **NOTE:** If the involved field is small, 7 days will be considered a sufficient interval between treatment and administration of the ixazomib

3.29b Known human immunodeficiency virus (HIV) positive.

- 3.29c Known hepatitis B surface antigen-positive status, or known or suspected active hepatitis C infection.
- 3.29d Any serious medical or psychiatric illness that could, in the investigator's opinion, potentially interfere with the completion of treatment according to this protocol.
- 3.29e Known allergies, hypersensitivity, or intolerance to corticosteroids, monoclonal antibodies or human proteins, or their excipients (refer to respective package inserts or Investigator's Brochure), or known sensitivity to mammalian-derived products.

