### Procedures for Reporting Drug Exposure During Pregnancy and Birth Events

If a woman becomes pregnant or suspects that she is pregnant while participating in this study or within 90 days after the last dose, she must inform the investigator immediately and permanently discontinue study drug. The sponsor-investigator must immediately fax a completed Pregnancy Form to the Takeda Department of Pharmacovigilance or designee (see Section 8.2). The pregnancy must be followed for the final pregnancy outcome.

If a female partner of a male patient becomes pregnant during the male patient's participation in this study, the sponsor-investigator must also immediately fax a completed Pregnancy Form to the Takeda Department of Pharmacovigilance or designee (see Section 8.2). Every effort should be made to follow the pregnancy for the final pregnancy outcome.

Suggested Pregnancy Reporting Form:

Pregnancy Report Form (provided by Takeda)

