Please refer to the Investigator's Brochure for a more comprehensive list of treatment-emergent adverse events.

**15.28 Drug procurement:** Commerical supply. Per standard requirements all physicians who prescribe lenalidomide for research subjects enrolled into this trial, and all research subjects enrolled into this trial, must be registered in and must comply with all requirements of the Celgene REVCLIMID REMS™ program. Prescriptions must be filled within 7 days. **Only enough lenalidomide for one cycle of therapy will be supplied to the patient each cycle.**

Any unused lenalidomide should be returned for disposition in accordance with the REVCLIMID REMS™ program

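### In 3.18, OR in place of AND makes the 90-day barrier commitment for men optional, so a non-abstinent man can qualify without it

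*Combined protocol and SAP*

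**What the plan says.** Section 3.18 gives separate contraception lists for women and men, and each patient has to agree to one item.

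- **Women:** the first item is dual contraception through 90 days after the last dose, with the programme clause attached inside the same item: "AND must also adhere to the guidelines of any treatment-specific pregnancy prevention program, if applicable, OR". The alternative is true abstinence.
- **Men:** there are three items. The first is "Agree to practice effective barrier contraception during the entire study treatment period and through 90 days after the last dose of study drug, OR". The second, standing alone, is "must also adhere to the guidelines of any treatment-specific pregnancy prevention program, if applicable, OR". The third is true abstinence.

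Adherence to the lenalidomide programme is required elsewhere of every patient. Section 3.19c lists "Willing to follow the requirements of the Revlimid REMS program" as its own inclusion criterion, and 15.28 says "all research subjects enrolled into this trial, must be registered in and must comply with all requirements" of the same programme.

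**The concern.** The list for men turns a two-part requirement into two alternatives. Every enrolled patient must follow the programme anyway, so every eligible man satisfies the second item. For a non-abstinent man, 3.18 then asks nothing that 3.19c does not already ask, and the 90-day commitment binds nobody.

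The stake is reproductive safety after treatment ends. Exclusion 3.23 justifies itself on the ground that "this study involves an investigational agent whose genotoxic, mutagenic and teratogenic effects on the developing fetus and newborn are unknown", and 10.62 says the effect of daratumumab on sperm is unknown. Lenalidomide stops after cycle 12 (7.3), but ixazomib and daratumumab continue in maintenance up to 36 months from registration (Table 7.1). The shorter period set in the lenalidomide appendix would then be the only stated post-treatment protection covering those two drugs in men.

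**Working it through.** The plan states no calculated figure to reproduce. The check is one of logic, followed by day counts.

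**1. Logic of the two lists**

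- Men, as written: (barrier to 90 days) OR (programme) OR (abstinence).
- Men, by parallel with the female list: [(barrier to 90 days) AND (programme)] OR (abstinence).

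Only the second form commits a non-abstinent man to 90 days. The word *also* in the male programme item has no sense in a stand-alone alternative, so the second form is evidently what was meant.

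**2. Does another section supply the 90 days for men?**

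| Section | What it gives for men |
|---|---|
| 3.23 | Excludes "Men or women of childbearing potential who are unwilling to employ adequate contraception"; no duration |
| 10.61, pregnancy reporting | The window "while participating in this study or within 90 days after the last dose" applies to women; for partners of men it covers only the man's participation |
| 15.29 | Condom use; no post-treatment period |
| Appendix V | Condom use during participation and for a minimum of 28 days after leaving the study |

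None does.

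**3. Size of the gap**

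Inputs: 90 days (3.18); 28 days after study discontinuation (Appendix V); 28-day safety period after the last cycle (7.0); no follow-up needed beyond 3 years from registration (4.2); treatment starts 0 to 14 days after registration (6.6); 28-day cycles with ixazomib last given on day 15 and maintenance daratumumab on day 1 (Table 7.1).

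*When nothing is lost.* The Appendix V period reaches day 90 if the man stays in the study for 90 − 28 = 62 days after his last dose. Three years is 1,095 days, and 1,095 − 62 = day 1,033, or 1,033 / 30.44 = 33.9 months. A man whose last dose falls before about month 34 and who stays in event monitoring, the normal route under 13.6, is fully covered.

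*On-schedule completer.* 1,095 / 28 = 39.1, so cycle 39 is the last full cycle. Its day 15 is 38 × 28 + 14 = 1,078 days after treatment start, which is day 1,078 to 1,092 after registration. That is past day 1,033. If he leaves the study after the safety period:

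- Last dose ixazomib, day 15: 13 days to cycle end + 28 + 28 = 69 days covered; 90 − 69 = **21 short**.
- Last dose daratumumab, day 1 (ixazomib stopped earlier, which 8.0 permits): 27 + 28 + 28 = 83 days covered; 90 − 83 = **7 short**.

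*Limit.* Exit on the day of the last dose leaves 28 days covered; 90 − 28 = **62 short**. In practice this means a refusal of further participation.

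**The case against.** The strongest reply is that this is a slip with a plain meaning. *Also* points back to the barrier item, the criterion is introduced as strict birth control, and 3.23 separately excludes men unwilling to use adequate contraception. Nothing shows that a site would read the list permissively. Appendix V and 15.29 still require condoms, and the 28 days are a floor. All of that is true, and no man is free of contraception on treatment. It does not supply the missing 90 days, and a safety criterion checked at registration should not depend on readers correcting it.

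The second reply concerns the day counts. The plan does not define when a man has discontinued the study. Section 4.2 says when follow-up is no longer required, not that participation ends. Section 10.61 asks for new malignancies to be reported for at least three years after the last dose. If that counts as participation, a completer who does not refuse has no gap. Footnote 13 in 4.1 requires HBV-DNA testing 12 weeks after the last dose in patients with evidence of prior infection. If those men are in the study until then, cover is 84 + 28 = 112 days. These points stand as limits on size, so the 7 and 21 days are conditional on exit after the safety period.

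Two further points stand. The consent pages and Appendix VIII might tell men 90 days; if they do, 3.18 disagrees with them. And correcting an eligibility criterion does not by itself reach men already registered.

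**Conclusion.** The concern holds: 3.18 is wrong as written for men, and the correction should be made. Taken literally, it never binds a non-abstinent man to the sponsor's own 90-day period, and nothing else in the supplied text does. Confidence is high on the wording.

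The practical effect is confined to the post-treatment tail. The loss is nil for men followed for at least 62 days after the last dose, 7 or 21 days for an on-schedule completer who leaves after the safety period, and at most 62 days. These figures assume that study discontinuation is the day the man leaves follow-up. The documents do not give the number of men affected. The list for women is correctly joined.

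**What to change.** In 3.18 only, merge the first two male items into one: effective barrier contraception for the whole treatment period and through 90 days after the last dose, AND adherence to any applicable pregnancy prevention programme. Keep true abstinence as the single alternative. This copies the structure of the female list.

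Appendix V and 15.29 need no change, since a 28-day minimum is compatible with 90 days. The cost is one connective in one eligibility criterion, with no effect on endpoint, sample size or analysis.
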